3.5 Myeloma patients and influenza

In myeloma patients on treatment, there is a 20% likelihood of influenza-like illness^{18,19} with a 10-fold higher risk of viral URIs²⁰ than the general population. Even patients with precancerous conditions such as monoclonal gammopathy of undetermined significance (MGUS) and Smoldering Myeloma are at increased risk of bacterial and viral infections²¹. While only 3-5% of these viral illnesses are influenza, the mortality is high in the immunosuppressed and post-influenza bacterial pneumonias have high morality. In addition myeloma and it's precursor diseases provide a novel window to studying vaccination in a full spectrum of immunosuppression from non-cancerous low-risk MGUS to end-stage lymphopenic patients with relapsed multiple myeloma.

Vaccine preventable illnesses have not been prevented in patients with myeloma due in part to lack of seroresponse with standard dosing algorithms. Based on available trial data restricted to myeloma patients, serologic protection (HAI titer ≥ 40) to all three influenza strains following trivalent influenza vaccine is achieved in less than 20% of myeloma patients in each trial²²⁻²⁴. There have been two trials investigating the benefit of booster vaccine in myeloma patients. In 2005 Ljungmen et al, studied 70 patients with hematologic malignancies (10 with myeloma and 4 with WM) and administered a booster dose 30 days following standard influenza vaccine booster and found no increase in serologic protection²⁵. More recently, in the past 2013-2014 flu season, Hahn et al gave a standard dose influenza booster vaccine after 30 days to 25 myeloma patients and noted a doubling of serologic protection (HAI titer ≥ 40) from 14% to 33%²⁶. This suggests that there may be a role for booster vaccines in patients with hematologic malignancies, however there is obviously much room to improve.

Prior studies by the [name] lab has evaluated serologic responses to repeat influenza vaccination in patients with plasma cell disorders. In the first SHIVERING trial, we analyzed a strategy of 2 vaccine Fluzone HD doses, which led to higher rates of seroprotection compared to historic controls²⁷. This was followed by a placebo-assisted randomized controlled study (SHIVERING-2 trial) comparing single dose versus 2-dose vaccination strategy. This trial²⁸ provided first evidence that 2-dose strategy leads to higher rates of seroprotection compared to current standard of annual influenza vaccination in these patients. At the end of the influenza season, the rates of sero-protection were 58% in the cohort with 2 vaccines versus 33% for the cohort with standard vaccines ($P<0.05$). These results

however need to be replicated in an independent study, before considering a change in standard practice. These considerations have led to the design of the current trial, wherein we will evaluate 3 doses of the vaccine (versus standard influenza vaccination) in order to further extend the rates of seroprotection at the end of study and test the hypothesis that repeat dosing of influenza vaccines leads to superior sero-protection in patients with plasma cell disorders, compared to that achieved with current standard vaccination strategy. If this trial replicates the findings with SHIVERING-2 trial, we believe it should lead to a change in current clinical practice for influenza vaccination in patients with plasma cell disorders.

3.6 Assessment of influenza vaccination response

Influenza vaccines work by activating antigen-specific B-cells to proliferate and differentiate into plasmablasts that secrete protective antibodies and memory B cells that can rapidly proliferate and differentiate into plasmablasts upon re-encountering the immunizing antigen. Studies in healthy individuals demonstrated a transient plasmablast response after vaccination peaking at around 7 days after vaccination at which point it makes up to 16% of all B-cell, and returning to baseline levels by day 14. Memory B-cell response, on the other hand, peaks at 14-28 days after vaccination followed by a slower rate of decline²⁹⁻³¹. A subset of the plasmablasts migrate to the bone marrow and become long-lived plasma cells secreting antigen-specific antibodies for protracted periods of time. Memory B-cell and plasma cells provide a remarkably stable immunological memory that can persist over 50 years after vaccination in humans. Interestingly, plasma cells are not intrinsically long-lived and only a finite number of plasma cells survive after an immune response irrespective of the number of plasma cells generated, suggesting that plasma cells require a specialized niche for survival³². It remains unclear what factors direct the differentiation of activated, antigen-specific B-cells into either memory B-cells or plasmablasts and plasma cells. Studies in mice suggested that the B-cell repertoire in the memory B-cell and the plasma cells compartments differ in terms of antigen-binding affinity and breadth³³.

Generation of immunological memory is the hallmark of adaptive immune responses. Clinically, this can be measured by determining seroprotection, defined as the percentage of subjects with a post-vaccination hemagglutination antibody inhibition (HAI) titer $> 1:40$; and seroconversion, the percentage of subjects with either a pre-vaccination HAI titer $< 1:10$ and a post-vaccination HAI titer $> 1:40$ or a pre-vaccination HAI titer $> 1:10$ and a minimum four-fold rise in post-vaccination HAI antibody titer by week 5.

Clearance of viral infection and vaccine responses are dependent on cell mediated immunity. The most common serologic measurement of antibody protection following influenza vaccine administration is an HAI titer of 40 or higher. However, this cutoff corresponds to an estimated 50% clinical benefit of preventing influenza infections, based on studies in young healthy adults^{34,35}. It is believed that cell-mediated immunity declines with age, which may help explain why the elderly are more vulnerable to influenza infections. HAI titers have also been shown to be lower in the elderly compared to young adults. Based on studies showing increased serologic protection, Fluzone HD (TIV) was FDA approved in 2009 for adults aged 65 and older, the QIV formulation in Nov-2019.

3.7 Study rationale

The challenge of decreasing influenza infection rate and severity in patients with hematologic malignancies are manifold: first, influenza virus undergoes antigenic drift and antigenic shift allowing it to overcome pre-existing immunity; second, the fact that most vaccine-elicited neutralizing antibodies are directed against hypervariable epitopes of the HA protein, facilitating the emergence of antibody-escape viral variants; third, the apparent short half-life of vaccine-mediated antibody titers in immunocompetent individuals; forth, the underlying immune suppressive state caused by the hematologic malignancy and worsened by the treatments that these patients need to receive; and fifth, the lack of high quality data looking at the response to influenza vaccination in patients with hematologic malignancy at the different stages of their disease course. Therefore, more studies are needed to define the optimal timing of influenza vaccination in patients with hematologic malignancies and to design an influenza vaccination strategy that provides a long-lived antibody response targeting a conserved epitope in HA.

The National Comprehensive Cancer Network still recommends yearly vaccination using an inactivated influenza vaccine with the hope of achieving some protection and decrease the severity in the event of an infection. It is presumed that the higher incidence of viral infections in patients with hematologic malignancies is due to immune suppression associated with treatment and poor rates of seroconversion after vaccination. However, the exact mechanism of how this occurs is not well understood, limiting our ability to design better preventive measures against influenza infection. This study will measure immune responses to influenza vaccination in patients with plasma cell dyscrasias.

3.8 Potential risks and benefits

3.8.1 Potential risks

1. **Additional blood draws** - The physical risk of drawing blood is local pain and bruising at the site of venipuncture. Qualified phlebotomists or designee will draw blood samples. Care will be taken to obtain these specimens in a safe and hygienic manner. A small number of people experience lightheadedness or fainting. There is a slight risk of infection. To minimize these risks, attempts will be made to draw study blood samples at the same time as blood draws needed for routine clinical care are obtained. Repeated blood drawing may be associated with iron deficiency anemia.
2. **Extra influenza vaccination** - The side effects from inactivated influenza vaccine are generally mild. They include soreness at injection site (10-64% of subjects) that lasts <2 days. When the vaccine is given, the subject may feel a slight pain and burning during the injection. Fever, malaise and myalgia can occur after vaccination with inactivated influenza vaccine. These reactions begin 6-12 hours after vaccination and can persist for 1-2 days. Patients with a history of severe allergic reaction are not eligible to participate in this study. Very rarely, occurring in about 1 in 4 million people given a vaccination, there can be a serious allergic reaction to a vaccine. These reactions can manifest as skin rash (hives), angioedema, bronchospasm, tachycardia, or hypotension. If these reactions occur, they can usually be stopped by the administration of emergency

medications by the study personnel. It is not known whether additional influenza risk will increase the risk of Guillain-Barre syndrome (GBS), estimated at 2.84 per million doses.

3. **Data security**- Subjects will be asked to provide personal health information (PHI). All attempts will be made to keep this PHI confidential within the limits of the law. However, there is a chance that unauthorized persons will see the subjects' PHI. All records will be kept in a locked file cabinet or maintained in a locked room at the participating sites. Electronic files will be password protected behind an academic institutional firewall. Only people who are involved in the conduct, oversight, monitoring, or auditing of this study will be allowed access to the PHI that is collected. Any publications from this study will not use information that will identify subjects. Organizations that may inspect and/or copy research records maintained at the participating sites for quality assurance and data analysis include groups such as the National Cancer Institute (NCI) and Food and Drug Administration (FDA).

3.8.2 Potential benefits

There is no guarantee of benefit to subjects who enroll in this protocol. However, seasonal influenza vaccine is considered beneficial to most subjects, as it generally provides protective immunity against the influenza strains within the vaccine. It is also considered standard of care for patients with hematologic malignancies. Data from this study may yield a better understanding of the current body of knowledge describing human infections with influenza viruses.

4. PATIENT SELECTION

4.1 Inclusion criteria

- 4.1.1 Patient must have a plasma cell dyscrasia that fits in the IMWG diagnostic criteria¹⁵.
- 4.1.2 Both men and women of all races and ethnic groups are eligible for this study.
- 4.1.3 Age \geq 18 years. Because plasma cell dyscrasias are extraordinarily rare in a pediatric population, children are excluded from this study.
- 4.1.4 ECOG performance status \leq 3 (Karnofsky \geq 30%, see Appendix A) is required for eligibility.
- 4.1.5 Patient must be eligible to receive standard of care influenza vaccination. If the patient has a history of egg allergy with symptoms more severe than urticaria, e.g. angioedema, respiratory distress, lightheadedness, or recurrent emesis, they remain eligible to receive influenza vaccination but must receive the vaccine in a facility able to recognize and manage severe allergic reactions. Persons who are able to eat lightly cooked egg

(e.g., scrambled egg) without reaction are unlikely to be allergic, although egg-allergic persons might tolerate egg in baked products

4.1.6 Ability to understand and the willingness to sign a written informed consent document.

4.2 Exclusion Criteria

4.2.1 Patients who have already received the seasonal influenza vaccine in the current season.

4.2.2 History of Guillain-Barré Syndrome

4.2.3 Patients with a previous severe allergic reaction to influenza vaccination or PCV13.

4.2.4 Expected survival < 9 months

4.2.5 Prisoners

5. REGISTRATION, ACCRUAL, AND EARLY TERMINATION

5.1 Accrual

5.1.1 Enrollment overall

The research team member obtaining informed consent will tell the patient that (1) participation is voluntary, (2) participation or non-participation will not affect their usual care and management, and (3) patient confidentiality will be maintained if the results of the study are published. The potential toxicities of protocol therapy and the study calendar will be explained to the potential participant. Patients will be provided with a consent form to review, and an opportunity to discuss the study and have all questions answered.

5.1.2 Registration Process

Patients will be registered after meeting all entry requirements and signing of the informed consent document.

To register a patient, the following should be completed

- Signed patient consent form
- HIPAA authorization form (if separate from consent form)

At Winship Cancer Institute [Emory], the research coordinator will verify eligibility per standard Clinical Trials Office procedures. To complete the registration process, the research coordinator will

- register the patient on the study
- assign the patient a study sequence ID

5.1.3 Strategies for recruitment and retention

This protocol follows NIH policy on inclusion of women and minorities as participants in research involving human subjects.

No incentives are provided to patients for trial participation.

5.1.4 Initial treatment arms

The total sample size of 148 patients will be split equally between the single versus 3-shot arms.

5.1.5 Method of treatment allocation

A patient number will be assigned upon registration.

5.1.6 Estimated accrual based on race, ethnicity and gender

Ethnic Category	Sex/Gender			
	Females		Males	Total
Hispanic or Latino	3	+	4	= 15
Not Hispanic or Latino	61	+	80	= 165
Ethnic Category: Total of all subjects	64	+	84	= 148
Racial Category				
American Indian or Alaskan Native	1	+	0	= 1
Asian	1	+	2	= 3
Black or African American	10	+	18	= 28
Native Hawaiian or other Pacific Islander	1	+	0	= 1
White	51	+	64	= 115
Racial Category: Total of all subjects	64	+	84	= 148

5.2 Duration of therapy

Patient may remain on study until one of the following criteria applies:

- Intercurrent illness that prevents administration of vaccine or follow-up,
- Per physician discretion in the setting of unacceptable adverse event(s), or other medical condition or situation occurs such that continued participation in the study would not be in the best interest of the participant. In patients who are randomized to the experimental arm only, specific adverse events include grade 3 adverse event that occurs without alternative etiology in the 7 days following the first study vaccination

- Patient decides to withdraw from the study, or
- General or specific changes in the patient's condition render the patient unacceptable for further treatment in the judgment of the PI.
- Termination or suspension of the study for safety reasons

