5.3 Duration of follow-up

Patients will be followed for 4 weeks after removal from study and patient records will be reviewed until death or 2 years from enrollment (whichever comes first) to assess progression and survival. Patients removed from study for unacceptable adverse event(s) will be followed until resolution or stabilization of the adverse event.

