5.4 Criteria for removal from study

Patients will be removed from study when any of the criteria listed in [Duration of therapy](#) applies. The reason for study removal and the date the patient was removed must be documented in the appropriate case report form.

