5.5 Early stopping rules

If there are any deaths possible, probably, or definitely related to protocol therapy, the trial will be suspended and the [DSMC](#) will provide recommendations for proceeding with the study to the PI.

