6.1.2 Control arm – Single Fluzone HD

Fluzone HD vaccine once at the time of enrollment for a total of 1 dose.

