10.2 Analysis datasets

Safety Population: The safety analysis dataset will include all eligible patients who begin treatment and receive at least one dose of protocol therapy. Patients will be analyzed in the cohort to which they were enrolled.

Efficacy Evaluable Population: All evaluable patients will be included in the analysis of efficacy endpoint. The term evaluable is defined as any eligible patient who receives at least one dose of protocol therapy and does not withdraw consent until the patient's first response assessment. Patients who fail to have a response assessment due to early progression or death will be categorized as non-responders.

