10.3 Sample size determination

In the initial design, the sample sizes of 81 in each group achieved 90% power to detect a difference between the group proportions of 0.2520. The proportion in group one (the intense Fluzone HD arm) is assumed to be 0.3330 under the null hypothesis and 0.5850 under the alternative hypothesis. The proportion in group two (the control group) is 0.3330. The test statistic used is the two-sided Z test with pooled variance. The significance level of the test (the alpha) was targeted at 0.0500, i.e. the probability of rejecting a true null hypothesis that was desired. The significance level

actually achieved by this design is 0.0513. The planned power was 0.9, i.e. the probability of rejecting a false null hypothesis. We assume 10% drop off rate in the study so that we planned to enroll 90 patients in each group.

During the first influenza season (2019-2020), we enrolled 50 patients of which only 23 were evaluable as 27 patients missed the week 21 study assessment due to COVID19.

We aim to complete the trial during the influenza season 2020-2021, and hence will need to control season as a confounder through a logistic regression model. A logistic regression of a binary response variable (e.g. HAI>40) on a binary independent variable (e.g. the treatment arms) with a sample size of 134 observations (of which the two treatment arms are evenly distributed) achieves 80% power at a 0.05 significance level to detect a change in the rate of HAI>40 from the baseline value of 0.333 to 0.585. This change corresponds to an odds ratio of 2.82. An adjustment was made since a multiple regression of the independent variable of interest on the other independent variables (e.g. the seasons) in the logistic regression obtained an R-Squared of 0.1. Hence we will need 67 patients in each randomized arm. After taking into account the expected 10% dropout rate, we plan to enroll 74 patients in each arm, producing a total sample size of 148 patients. Given we already accrued 11 evaluable patients per arm during the first season, we will plan to enroll an additional 125 patients in the second season.

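### As written, a safety suspension that may be lifted removes all patients still on study, leaving those before about day 107-112 with no provision for the week-21 HAI endpoint

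*Combined protocol and SAP*

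**What the plan says.** Section 5.2 lists the events that end a patient's time on study. The last is "Termination or suspension of the study for safety reasons". Section 5.4 is mandatory: "Patients will be removed from study when any of the criteria listed in" section 5.2 applies. Section 5.3 sets what happens next: "Patients will be followed for 4 weeks after removal from study", followed by record review, up to 2 years from enrollment, for progression and survival.

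Section 5.5 is the trial's own stopping rule: "If there are any deaths possible, probably, or definitely related to protocol therapy, the trial will be suspended". The DSMC then "will provide recommendations for proceeding with the study to the PI", so the trial may go on.

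Section 1 makes seroprotection at week 21 the primary comparison, and 6.5 schedules research blood at baseline, week 5 and week 21 in both arms. Controls receive "Fluzone HD vaccine once at the time of enrollment for a total of 1 dose" (6.1.2). On missing outcomes, 10.2 says only this: "Patients who fail to have a response assessment due to early progression or death will be categorized as non-responders". Section 10.3 reports that in the first season "only 23 were evaluable as 27 patients missed the week 21 study assessment due to COVID19".

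Section 10.4.2 refers to the stopping rules as a temporary halt to enrollment, a narrower scope than the whole trial named in 5.5.

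**The concern.** A suspension for review and a termination are different events, but 5.2 treats them alike. If one death is rated at least possibly related, 5.5 suspends the trial. Sections 5.2 and 5.4 then take every patient still on study off it. If the DSMC later advises going on, no section brings those patients back or provides an HAI draw for them at week 21.

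The rule makes no distinction by arm. For a control patient, removal withholds no further Fluzone HD, because the only dose was given at enrollment. It gives up a titer that was already scheduled. Nor does 10.2 say how such a patient is counted, since the titer is missing for neither progression nor death. Section 10.3 treated first-season patients who missed week 21 as not evaluable.

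At stake are primary outcomes in both arms of a trial that was re-sized after losing 27 of 50 week-21 assessments in its first season. The trigger is a single event, and 11.3 gives reasonable timing after vaccination as its example of evidence for a possible relation.

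**Working it through.** **Plan's own figure.** Inputs from 10.3: 0.333 versus 0.585, alpha 0.05, 80% power, R-squared 0.1. The test is taken as two-sided, which 10.3 states for the initial design. The logistic sample-size formula for a balanced binary covariate gives 120.4, and 120.4 / (1 - 0.1) = 133.8, so 134 as stated. A pooled two-proportion Z test with n per arm = 0.9 × N / 2 gives 80.1% at N = 134. The same approximation is used below.

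**Who is affected.** Visits are counted from the first Fluzone HD dose with a 5-day window either way (6.5). With week 1 as day 0, week 21 is 20 × 7 = day 140, and its window opens on day 135. Post-removal follow-up is 28 days.

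- To reach the opening of the window: 135 - 28 = day 107.
- To reach the nominal visit: 140 - 28 = day 112.

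Reading week 21 as 21 full weeks moves the range to 114-119. The cut-off is lenient, because 5.3 names no HAI draw even within the four weeks. For a patient dosed on 15 December 2020, day 107 is 1 April 2021.

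**Illustration of size.** The documents give no opening date for the second season. Assumptions: 125 patients enrolled uniformly to 15 December 2020, opening on 1 August (136 days) or 1 October (75 days); 10% dropout, so 0.9 × 125 = 112.5 expected titers; the 23 first-season titers kept; day-107 cut-off. A titer is lost if enrollment falls later than 107 days before suspension. Remaining N = 23 + 112.5 × (1 - share lost).

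| Suspension | Share lost | Titers lost | Of these, controls | Remaining N | Power as written |
|---|---|---|---|---|---|
| 15 Jan 2021 | 76/136 = 56% to 100% | 63-112 | 31-56 | 72.6 to 23 | 53% to 20% |
| 15 Feb 2021 | 45/136 = 33% to 45/75 = 60% | 37-68 | 19-34 | 98.3 to 68 | 67% to 51% |
| 15 Mar 2021 | 17/136 = 12.5% to 17/75 = 23% | 14-26 | 7-13 | 121.4 to 110 | 76% to 72% |
| 1 Apr 2021 or later | 0 | 0 | 0 | 135.5 | 81% |

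**What keeping patients on study would do.** All 135.5 titers are then kept, but the experimental arm may have missed doses. Dose 2 is due on day 56 and dose 3 on day 112. If withheld doses stay withheld, the experimental rate becomes 0.585 - 0.252 × (112.5/135.5) × the share of second-season patients affected.

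- Doses given later and working as planned: power 81%.
- Doses stay withheld, two doses as good as three (3.5 reports 58% with two doses against 33%): only patients with a single dose are affected, 18-33% on 15 January and none later. Power is 53-67% on 15 January and 81% on the later dates.
- Doses stay withheld, two doses no better than one: the shares without dose 3 are 60-100%, 37-67% and 16-29% on the three dates. Rates fall to 0.460-0.376, 0.508-0.446 and 0.551-0.524. Power is 30-7%, 50-25% and 68-57%, below the as-written column.

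**The case against.** The strongest reply is that nobody meant this. Section 10.4.2 describes the stopping rule as a temporary halt to enrollment, which would leave enrolled patients alone. Sections 1 and 6.5 plan week-21 blood for everyone, and the 5.2 bullet pairs suspension with termination, so it may have had closure in mind. A reader might infer from 5.2 and 5.4 that the plan deliberately discards patients during a short pause; the documents do not support that. What remains is a conflict: 5.5 suspends the trial, 5.2 and 5.4 are explicit and mandatory, and a descriptive phrase in 10.4.2 does not override them. Staff following 5.4 would remove patients.

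Second, nothing in 5.3 forbids a later draw, and the trial has already replaced lost patients with a second season. Both points are fair. But an unscheduled draw depends on someone improvising it, a titer taken late is not the week-21 endpoint, and another season costs time.

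Third, the other 5.2 criteria (illness, adverse events, investigator judgment) lead to the same removal, and 10.2 is equally silent on them. That is true, and the change below does not cure it. Those criteria act on individual patients, whereas a suspension acts on all of them at once and is the case in which the trial may restart.

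Fourth, enrollment is to be as early as possible in the season, so uniform accrual to 15 December may overstate the losses. This stands, and is one reason the table is illustration only.

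**Conclusion.** The point stands on the text. A safety suspension that the DSMC may advise lifting removes all patients still on study, and those before about day 107-112 then have no provision for the week-21 titer and no assigned outcome, in either arm. It is a drafting conflict, probably unintended, and it matters only if a suspension occurs.

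Its size cannot be fixed from the documents. It runs from nothing (suspension from 1 April 2021) to every second-season titer (suspension in mid-January with an October opening), under the assumed accrual.

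Three stronger readings should be resisted. A reader might infer that such a suspension is likely. The documents give neither a mortality rate for this population nor the share of deaths that would be rated possibly related, and 7.1.5 says a fatal reaction is not expected, so no probability is offered here. A reader might infer that keeping patients on study restores 80% power. It may not: if withheld doses are never given and two doses do no better than one, power falls below the as-written figure. A reader might also infer bias between the arms. The rule removes both arms alike according to enrollment date, so the direct consequence is lost information. The gain from a change is that obtainable primary outcomes are kept.

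**What to change.** In 5.2, strike *or suspension* from the bullet "Termination or suspension of the study for safety reasons", so that only termination ends time on study.

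Add to 5.5: *A suspension under this section pauses new enrollment and all outstanding protocol vaccinations (Fluzone HD and protocol-scheduled PCV13) until the DSMC recommends otherwise. Unless the DSMC, IRB or other suspending party directs that research procedures stop, enrolled patients stay on study and scheduled week-5 and week-21 research bloods, adverse event and influenza-like illness contacts continue. Withheld doses are recorded, and patients are analyzed in their randomized arm.*

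In 10.4.2, refer to a temporary suspension of the trial rather than of enrollment, and point to 5.5.

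PCV13 is included because it is a protocol vaccine at week 5 in both arms and should not continue while a possibly related death is under review. The override clause leaves the DSMC and others free to stop research procedures.

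The cost is wording in three sections. There are no new visits or samples, because these bloods and contacts are already scheduled, and the required N is unchanged. The downside is that doses withheld during a pause may dilute the difference between arms.
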